8.2.1.2. Post-infusion systemic reactions by infusion

For the TH group in the RS phase, summaries of post-infusion systemic reactions will be presented by the first six infusions in the RS phase and PT for the following categories:

- Post-Infusion Systemic Reactions per Anaphylactic Reaction CMQ broad search (on the day of the infusion or within 3 days after the infusion)
- Serious Post-Infusion Systemic Reactions per Anaphylactic Reaction CMQ broad search (on the day of the infusion or within 3 days after the infusion)
- Serious Acute Post-Infusion Systemic Reactions/Hypersensitivity per GSK adjudication
- Serious Delayed Acute Hypersensitivity Reactions per GSK adjudication
- Serious Delayed Non-Acute Hypersensitivity Reactions per GSK adjudication

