5. STUDY TREATMENTS

5.1. Investigational Product and Other Study Treatment

Belimumab for intravenous (IV) infusion will be supplied in glass vials by GSK. The contents of the label will be in accordance with all applicable regulatory requirements. Detailed instructions on the preparation, administration and storage of belimumab are provided in the Pharmacy Manual. Belimumab IV solution should be prepared by a pharmacist. Reconstitute the 400 mg single use vial of belimumab with 4.8 mL sterile water for injection to yield a final concentration of belimumab 80 mg/mL. Remove an amount of normal saline from the infusion bag equivalent to the amount of belimumab to be added, add the reconstituted belimumab, and gently invert the infusion bag to mix the solution. After reconstitution and dilution in normal saline, the material is stable for up to 8 hours at 2-8°C or at room temperature. The characteristics of belimumab are summarized in Table 1.

Property	Belimumab
Formulation	Belimumab 400 mg per vial plus excipients (citric
	acid/sodium citrate/sucrose/polysorbate)
Dosage Form	Reconstituted solution
Unit dose strength	400 mg per vial (to contain 80 mg/mL when reconstituted
	with 4.8mL sterile water for injection [SWFI])
Physical description	White uniform lyophilised cake in a 20 mL vial
Manufacturer	Human Genome Sciences, Inc.
Route of administration	Intravenous

Table 1 Belimumab Characteristics

Subjects enrolled in the treatment holiday group will receive treatment with belimumab 10 mg/kg from Week 24 onwards **after** the initial 24-week treatment holiday period of the study has elapsed (see Section 3.1). At the start of the belimumab reintroduction period, subjects in the treatment holiday group will receive belimumab 10 mg/kg IV infused for over 1 hour every 28 days.

Subjects in the control group will receive belimumab 10 mg/kg IV infused for over 1 hour every 28 days from Day 0 onwards. Subjects in this group must be able to receive their first dose of belimumab on Day 0 of this study 4 weeks (minimum of 2 weeks, maximum of 8 weeks) after the last dose in the BEL114333 open-label continuation study.

Subjects in the long-term discontinuation group will not receive belimumab at any point in this study.

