2.3. Study Design

Overview of Study Design ar	Overview of Study Design and Key Features	
	this long-term safety data to regulatory authorities in the initial BLA and other marketing authorization submissions). Additional interim analyses may be required to support subsequent safety updates to regulatory authorities. No interim analyses were conducted.	
Sample Size	• The total target sample size was 71 subjects and 80 were enrolled. The target sample size for subjects in the treatment holiday and control groups was 10 (12 enrolled) and 26 (29 enrolled) subjects respectively. A target sample size of 35 (39 enrolled) subjects in the long-term discontinuation group was anticipated.	

Note: Subjects from China participated in BEL113750 OL phase rather than in BEL114333, and were therefore eligible to enter BEL116027 from BEL113750 OL, per a China country-specific protocol amendment 01.

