2.4. Statistical Hypotheses / Statistical Analyses

Since this is a non-randomized study, results will be descriptive only, and any comparisons are not intended to be inferential.

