8.2.2. Summary Measure

8.2.2.1. Adverse Events of Special Interest

An overall summary of AESIs by category will be presented, and each specific category of AESI will be presented separately by PT. The number and percentage of subjects with at least one occurrence and the number of events will be presented.

Infection AESIs that are serious, severe, serious/severe, and that lead to discontinuation will be presented by category and PT.

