Y	'Y' if CMSCAT ne blank and the route of administration is "INTRADERMAL" "PO" "INTRAMUSCULAR", "INTRAVENOUS", "ORAL", or "SUBCUTANEOUS"
Ν	'N' otherwise and CSMCAT ne blank

Treatment Compliance

• Treatment compliance for patients completing the 52 week treatment phase or withdrawals is calculated as:

treatment compliance (%)

- $= 100 \times \frac{Number \ of \ infusions \ prescribed Number \ of \ infusions \ missed}{Number \ of \ infusions \ prescribed}$
- Prescribed number of infusions will be 7 for the TH arm and 13 for the TC arm, except for TH subjects who escape to the Maintenance Phase. For TH subjects who escape, the treatment compliance will be missing. The Week 52 infusion is considered to be the first infusion of the maintenance phase.
- NB: for withdrawals the number of infusions prescribed is the number from Day 0 up to the withdrawal date

Extent of Exposure

Number of days of exposure to study treatment during the 52-week Treatment Phase will be calculated based on the formula:

Duration of Exposure in Days = (Date of last infusion in BEL116027 52-week treatment Phase– Date of first infusion in BEL116027) + 28

- The Week 52 infusion is considered to be the first infusion in the Maintenance Phase, and will not be considered in this calculation.
- Subjects who were enrolled in the TH and TC groups but did not receive an infusion will be categorised as having zero days of exposure.
- Exposure will not be calculated for the LTD group.
- Only complete dates will be used when calculating duration of exposure.
- Exposure will not be adjusted for skipped infusions.

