13.11.7. Safety Tables

Safety:	Safety: Tables					
No.	Population	Title	Programming Notes	Priority Headline Results Denoted by H		
Concor	mitant Medicati	ons				
3.1.	ITT	Concomitant Medications by ATC Level 1 and ATC Level 4 Term for the 52-Week Treatment Phase	ICH E3			
Study A	Agent Exposure	9				
3.2.	ITT	Study Agent Exposure (52-Week Treatment Phase)	ICH E3			
SLICC						
3.3.	ITT	SLICC/ACR Damage Index Change from Baseline (52- Week Treatment Phase)	Other/exploratory endpoint			
Advers	e Events		·			
3.4.	ITT	Adverse Events (52-Week Treatment Phase)	Benlysta standard	Н		
3.5.	ITT	Adverse Events by SOC (52-Week Treatment Phase)	Benlysta standard			
3.6.	ITT	Serious Adverse Events by SOC (52-Week Treatment Phase)	Benlysta standard			
3.7.	ITT	Study Agent Related Adverse Events by SOC (52-Week Treatment Phase)	Benlysta standard			
3.8.	ITT	Adverse Events Resulting in Study Agent Discontinuation by SOC (52-Week Treatment Phase)	Benlysta standard			

Safety:	Safety: Tables				
No.	Population	Title	Programming Notes	Priority Headline Results Denoted by H	
3.9.	ITT	Adverse Events by SOC and PT (52-Week Treatment Phase)	ICH E3	Н	
3.10.	ITT	Serious Adverse Events by SOC and PT (52-Week Treatment Phase)	Benlysta Standard	Н	
3.11.	ITT	Study Agent Related Adverse Events by SOC and PT (52-Week Treatment Phase)	ICH E3		
3.12.	ITT	Adverse Events Resulting in Study Agent Discontinuation by SOC and PT (52-Week Treatment Phase)	IDSL	Н	
3.13.	ITT	Adverse Events by PT (52-Week Treatment Phase)	Benlysta Standard		
3.14.	ITT	Serious Adverse Events by PT (52-Week Treatment Phase)	Benlysta Standard		
3.15.	ITT	Study Agent Related Adverse Events by PT (52-Week Treatment Phase)	Benlysta Standard		
3.16.	ITT	Adverse Events Resulting in Study Agent Discontinuation by PT (52-Week Treatment Phase)	Benlysta Standard		
3.17.	ІТТ	Common (>5%) Non-Serious Adverse Events by SOC and PT (52-Week Treatment Phase) (Number of Subjects and Occurrences)	FDAAA, EudraCT		
3.18.	ІТТ	Serious Adverse Events by SOC and PT (52-Week Treatment Phase) (Number of Participants and Occurrences)	FDAAA, EudraCT	Н	
3.19.	ITT	Adverse Events by SOC and PT and Maximum Severity (52- Week Treatment Phase)	IDSL		

Safety:	afety: Tables					
No.	Population	Title	Programming Notes	Priority Headline Results Denoted by H		
3.20.	ITT	Relationship Between System Organ Class and Verbatim Text (52-Week Treatment Phase)	IDSL			

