3.21.	ITT	Adverse Events of Special Interest by Category (52-Week Treatment Phase)	Benlysta Standard	н		
3.22.	ITT	Adverse Events of Special Interest by Category and Infusion for Treatment Holiday Group Re-Start Phase	Benlysta Standard			
Labora	tory Parameter	'S				
3.23.	ITT	Laboratory Results by Visit: Hematology (52-Week Treatment Phase				
3.24.	ITT	Laboratory Results by Visit: Liver Function (52-Week Treatment Phase)				
3.25.	ITT	Laboratory Results by Visit: Electrolytes (52-Week Treatment Phase)				
3.26.	ITT	Laboratory Results by Visit: Other Chemistries (52-Week Treatment Phase)				
3.27.	ITT	Laboratory Results by Visit: Urinalysis (52-Week Treatment Phase)				
3.28.	ITT	Laboratory Results by Visit: Immunoglobulins (52-Week Treatment Phase)				
3.29.	ITT	Worst Laboratory Toxicity Grade: Hematology (52-Week Treatment Phase)	ICH E3			

Safety:	Tables			
No.	Population	Title	Programming Notes	Priority Headline Results Denoted by H
3.30.	ITT	Worst Laboratory Toxicity Grade: Liver Function (52-Week Treatment Phase)	ICH E3	
3.31.	ITT	Worst Laboratory Toxicity Grade: Electrolytes (52-Week Treatment Phase)	ICH E3	
3.32.	ITT	Worst Laboratory Toxicity Grade: Other Chemistries (52-Week Treatment Phase)	ICH E3	
3.33.	ITT	Worst Laboratory Toxicity Grade: Urinalysis (52-Week Treatment Phase)	ICH E3	
3.34.	ITT	Worst Laboratory Toxicity Grade: Immunoglobulins (52-Week Treatment Phase)	ICH E3	
3.35.	ITT	Laboratory Toxicity Grade Worsening of at Least 2 Grades from Baseline: Hematology (52-Week Treatment Phase)	Benlysta Standard	
3.36.	ITT	Laboratory Toxicity Grade Worsening of at Least 2 Grades from Baseline: Liver Function (52-Week Treatment Phase)	Benlysta Standard	
3.37.	ITT	Laboratory Toxicity Grade Worsening of at Least 2 Grades from Baseline: Electrolytes (52-Week Treatment Phase)	Benlysta Standard	
3.38.	ITT	Laboratory Toxicity Grade Worsening of at Least 2 Grades from Baseline: Other Chemistries (52-Week Treatment Phase)	Benlysta Standard	
3.39.	ITT	Laboratory Toxicity Grade Worsening of at Least 2 Grades from Baseline: Urinalysis (52-Week Treatment Phase)	Benlysta Standard	
3.40.	ITT	Laboratory Toxicity Grade Worsening of at Least 2 Grades from Baseline: Immunoglobulins (52-Week Treatment Phase)	Benlysta Standard	
3.41.	ITT	Laboratory Reference Range Shifts from Baseline by Visit: Hematology (52-Week Treatment Phase)	Benlysta Standard	

Safety: Tables				
No.	Population	Title	Programming Notes	Priority Headline Results Denoted by H

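### Post-infusion reactions after re-introduction have no exposure-aligned comparison with control: the all-group table sets 7 planned holiday infusions against 13 control infusions

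*SAP*

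**What the plan says.** SAP 8.2.1.2 plans the by-infusion summary for one group: "For the TH group in the RS phase, summaries of post-infusion systemic reactions will be presented by the first six infusions". The display list carries this through as Table 3.22, "Adverse Events of Special Interest by Category and Infusion for Treatment Holiday Group Re-Start Phase", and Appendix 11 contains no TC counterpart.

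All groups meet in Table 3.21, a headline table of adverse events of special interest by category over the 52-week phase in the ITT population. SAP 8.2.2.1 defines its measure: "The number and percentage of subjects with at least one occurrence and the number of events will be presented". No per-infusion or exposure denominator is given.

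The number of infusions differs by design. SAP 13.6.2 states: "Prescribed number of infusions will be 7 for the TH arm and 13 for the TC arm". The Week 52 infusion is counted in the maintenance phase. Under SAP 13.9.2 a reaction qualifies only if it falls on the infusion day or in the three days that follow, so exposure to the risk is counted in infusions.

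Protocol 8.1.4 commits to AE numbers and incidence by 6-month interval, and allows rates adjusted for time on study agent. Neither appears in SAP Appendix 11. SAP 2.1, which lists changes from the protocol, does not record dropping the interval summary.

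**The concern.** Re-introduction after a drug-free period is part of what this study is meant to describe. Protocol 6.4.12 asks for extended observation of TH subjects after their first two re-start infusions. Readers will want to know whether reactions are more frequent when belimumab is resumed than when it is continued.

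Table 3.22 gives the TH experience with nothing beside it. Table 3.21 puts TC beside TH, but TC subjects have nearly twice as many opportunities for an event that can arise only after an infusion. The imbalance works in one direction. A real excess per infusion after the holiday could be displayed as no difference, or as a lower percentage, in a headline table.

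**Working it through.** **Inputs**
- Planned infusions: TH 7, TC 13 (SAP 13.6.2).
- Enrolled: TH 12, TC 29 (SAP 2.3: "groups was 10 (12 enrolled) and 26 (29 enrolled) subjects respectively").
- Benchmark: about 17% of belimumab patients had an infusion-related reaction in earlier double-blind studies, against 15% on placebo (Protocol 6.4.12). Applying 17% to 13 infusions is my assumption. The documents give no per-infusion risk, so I show a range.

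**Reproducing the plan's figures.** Four-weekly visits from Week 24 to Week 48 give 7. From Week 0 to Week 48 they give 13. Both match. From Week 24 onwards TC also has 7.

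**Events per subject.** At a common per-infusion risk p, the ratio is 7p/13p = 0.54 for any p.

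**Subjects with at least one event.** With independent, constant risk, P = 1 − (1 − p)^k, with k = 7 or 13:

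| p | TH, k = 7 | TC, k = 13 | Ratio |
|---|---|---|---|
| 0.1% | 0.70% | 1.29% | 0.54 |
| 0.5% | 3.45% | 6.31% | 0.55 |
| 1% | 6.8% | 12.2% | 0.55 |
| 2% | 13.2% | 23.1% | 0.57 |
| 5% | 30.2% | 48.7% | 0.62 |
| 10% | 52.2% | 74.6% | 0.70 |

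**Benchmark case.** If 17% of TC react over 13 infusions, p = 1 − 0.83^(1/13) = 1.42%. Over 7 infusions the same risk gives 1 − (1 − 0.01423)^7 = 9.5%, a ratio of 0.56. For TH to reach 17% over 7 infusions, its per-infusion risk must be 1 − 0.83^(1/7) = 2.63%, and 2.63/1.42 = 1.85 times that of TC.

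**A truly doubled risk.** The planned table would show 1 − (1 − 2 × 0.01423)^7 = 18.3% for TH against 17.0% for TC. Set against 7 TC infusions, it would be 18.3% against 9.5%, a ratio of 1.92.

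**Clustering within subjects.** Under a beta-binomial with mean p from 0.5% to 5% and intraclass correlation from 0.05 to 0.3 (both assumed), the ratio of subject percentages runs from 0.61 to 0.78. For example, mean p = 1.4% with correlation 0.1 gives 7.3% against 11.1%, a ratio of 0.66.

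**The 7 is a ceiling.** TH subjects who never re-start stay in the ITT denominator. If 2 of 12 had no re-start infusions (assumption), mean infusions per subject are 7 × 10/12 = 5.83, and 5.83/13 = 0.45.

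**Phase assignment.** SAP 13.4.1 places an event dated on a phase cut-point in the preceding phase. For TH the cut-point is the Week 24 or re-start visit. Read literally, a same-day reaction to the first re-start infusion belongs to the Holiday Phase and could be missing from Table 3.22.

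**The case against.** The strongest reply is that the SAP makes no inferential claim: "results will be descriptive only, and any comparisons are not intended to be inferential". With 12 TH subjects, one subject is 1/12 = 8.3 percentage points, more than the 17 − 9.5 = 7.5 point artefact in the benchmark case. The 17% counts day-of-infusion events at 1 or 10 mg/kg, whereas subjects here have had at least 6 months of belimumab and the SAP window is longer. Protocol 6.4.12 does not say that a drug-free gap raises risk. The first re-start infusion also has no true counterpart in continuously treated controls. All of this stands, and it limits how much any version of the table can show. It does not justify a headline table whose columns differ by design in opportunities for the event. The 0.54 ratio for events per subject does not depend on the 17%.

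A reader might infer that there is no comparator at all. The documents do not support that. Table 3.21 is an ITT table giving event counts as well as percentages, Table 3.2 reports exposure, and Listings 12 and 25 would allow a match after the fact. What is missing is a planned, aligned comparison.

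A reader might also infer that the long-term discontinuation (LTD) group contributes misleading zeros, here and in Table 3.12 ("Adverse Events Resulting in Study Agent Discontinuation by SOC and PT (52-Week Treatment Phase)". It is true that "Subjects in the long-term discontinuation group will not receive belimumab at any point in this study". However, SAP 5.1 says some tables will show only TC and TH, and the table shells are not in the documents, so whether such zeros are printed is unknown. Whether an AE that prevents re-start counts as discontinuation of study agent depends on the eCRF, which is also not available.

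**Conclusion.** The point holds as a reporting weakness that should be corrected. The SAP plans no comparison of post-infusion reactions in which TH and TC have the same opportunity for the event, and the imbalance favours re-introduction.

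A reader might summarise the effect as a near-halving without qualification. That is right for events per subject (0.54 at equal per-infusion risk). For subject percentages it needs low, independent risk: 0.54 to 0.57 for TC cumulative risk up to about 23%, weakening to about 0.6 to 0.8 if reactions cluster. These figures assume full planned dosing and constant risk.

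Unseen shells might split TH by phase in Table 3.21, but a re-start column would still hold 7 infusions against 13. The protocol's 6-month summary would roughly align the periods, but it is absent from the display list.

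**What to change.** 1. In Table 3.21 or a companion table, report post-infusion reactions per 100 infusions given, for TC and TH. Planned denominators at enrolled numbers are at most 29 × 13 = 377 and 12 × 7 = 84.
2. Beside Table 3.22, show TC reactions for infusions from Week 24 onwards, with the denominator at each infusion being the subjects who received it. Label this a descriptive reference for continuous treatment. Protocol 4.4 allows a first re-start infusion after Week 24, so calendar week and re-start infusion number will not always coincide; state which is used.
3. Assign each post-infusion reaction to the infusion that preceded it, overriding the cut-point rule in SAP 13.4.1, so that same-day reactions to the first re-start infusion fall in the Re-start phase. Do not mark the Holiday Phase as not applicable for these reactions: under the present rule that would remove those very events.
4. Restore the 6-month AE summary of Protocol 8.1.4, or record its omission in SAP 2.1.
5. At most, add a footnote that LTD received no study agent.

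The cost is SAP wording and a few table columns. Infusion and AE dates are already collected and listed. If outputs already exist, label the additions as post hoc.

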8.2.2. Summary Measure

8.2.2.1. Adverse Events of Special Interest

An overall summary of AESIs by category will be presented, and each specific category of AESI will be presented separately by PT. The number and percentage of subjects with at least one occurrence and the number of events will be presented.

Infection AESIs that are serious, severe, serious/severe, and that lead to discontinuation will be presented by category and PT.

8.2.2.2. Post-infusion systemic reactions by infusion

The number and percentage of subjects with at least one occurrence and the number of events will be presented.

8.2.3. Population of Interest

The analyses will be based on the ITT population.

8.2.4. Strategy for Intercurrent (Post-Randomization) Events

For both endpoints, observed data will be used with no imputation.

8.2.5. Statistical Analyses / Methods

Details of the planned displays are provided in Appendix 11: List of Data Displays and will be based on GSK data standards and statistical principles.

Unless otherwise specified, endpoints / variables defined in Section 8.2.1 will be summarised using descriptive statistics, graphically presented (where appropriate) and listed.

8.3. Clinical Laboratory Analyses

Laboratory evaluations including the analyses of chemistry laboratory tests, hematology laboratory tests, urinalysis, and liver function tests will be based on GSK Core Data Standards. The details of the planned displays are in Appendix 11: List of Data Displays.

An issue was identified at Q2 Solutions (central lab) in Valencia, California, USA, regarding equipment malfunction which affected some serum creatinine results reported from one of the analyzers used at the lab. Unusually high serum creatinine results were noted for two different GSK clinical trials, and further investigation revealed one of the analyzers had been producing intermittent high serum creatinine results between 01 October 2016 to 13 January 2017, potentially due to an intermittent wash line blockage of the analyzer. BEL116027 investigators were notified of this issue by a Dear Investigator Letter (DIL) 22 February 2017. The subsequent evaluation concluded that there was no impact on data integrity and patient safety for clinical trial BEL116027. Therefore, there will be no modification to the analysis of serum creatinine. BEL116027 investigators were notified by a follow up DIL dated 25 July 2017, and the root cause was identified as a sporadic failure of the wash system due to debris causing intermittent obstruction.

Baseline is defined as described in Section 5.2.

A list of laboratory parameters collected and definition of the toxicity grades are provided in Appendix 8: Values of Potential Clinical Importance.

Listings will be generated for all laboratory results, and additionally for Grade 3 or Grade 4 laboratory toxicity results.

Line graphs will be produced for each analyte displaying the mean value by visit and treatment group.

8.3.1. Endpoint / Variables

8.3.1.1. Clinical Laboratory Results

Laboratory parameters which are continuous numeric values will be analyzed using summary statistics, and those with categorical results will be summarized using frequencies and percentages.

8.3.1.2. Clinical Laboratory Toxicity Grades

The endpoints evaluated will be:

- Worst toxicity grade
- Worsening by at least 2 toxicity grades

Toxicities will be reported as derived by the central laboratory, as protocol toxicity grading was applied.

For potassium, glucose, calcium, and sodium, toxicities are bi-directional (i.e., high and low directions) and both will be summarized by name of the toxicity.

- Potassium: hypokalemia, hyperkalemia
- Glucose: hypoglycemia, hyperglycemia
- Calcium: hypocalcemia, hypercalcemia
- Sodium: hyponatremia, hypernatremia

For example, calcium will have two toxicity sections, one for hypocalcemia and one for hypercalcemia and mapped to their high or low form as:

- RESULT < (LLN+ULN)/2 = "Hypo" toxicity
- RESULT > (LLN+ULN)/2 = "Hyper" toxicity

8.3.1.3. Clinical Laboratory Reference Range Shifts

For laboratory tests without toxicity grades, shifts relative to the normal range will be summarized for each analyte as shifts 'to low' and shifts 'to high.'

For the 'to low category' the percentage of subjects with at least one low post-baseline value relative to the baseline (i.e. baseline and post baseline data available) will be displayed using the categories: no shift to low and normal/high to low.

For the 'to high category' the percentage of subjects with at least one high post-baseline value relative to baseline (i.e. baseline and post baseline data available) will be displayed using the categories: no shift to high and normal/low to high.

A laboratory value that is above the testing laboratory's normal range will be considered a high abnormal laboratory value. A laboratory value that is below the testing laboratory's normal range will be considered a low abnormal value.

